#### 2.5.4 Vision Function Assessment

[figure not shown]
For the extraocular muscle function test and confrontation visual field vision function assessments (specified in Section 1.5.2) the number and percentage of subjects reporting normal and abnormal test results will be presented by treatment group and by visit.

For Snellen visual acuity test, subjects that experience a worsening of 1+ line change in at least one eye during the course of the study will be summarized by eye, treatment group, and visit. Only subjects that experience a worsening line change will be considered in the analysis; the number and percentage of subjects that experience a worsening of 1+ line change in at least one eye during the course of the study will be presented. The number of subjects with a non-missing Snellen assessment at a respective visit will be used as the denominator.

A 1+ worsening line change in Snellen visual acuity is when a subject moves up at least one line of letters on the Snellen Eye Chart (Figure 1). For example, if a subject's visual acuity at baseline is 20/40 for the left and right eyes and then at Visit 3 is 20/70 for the left eye and 20/50 in the right eye, the subject experienced a 2-line worsening for the left eye and a 1-line worsening in the right eye.

Figure 1. Snellen Eye Chart

2022-08-17 17:26

The visual function assessment data will also be presented by treatment and subject in data listing. This listing will only include subjects with a change in visual function as determined by any of the three vision assessments.

#### 2.5.5 Laboratory Assessments

The pregnancy test data will be presented by treatment and subject in a data listing.

#### 2.5.6 Device Deficiencies

A device deficiency is defined as an inadequacy of a medical device with respect to its identity, quality, durability, reliability, safety, or performance. Any reported device deficiency will be presented by subject in a data listing.

#### 2.6 Interim Analysis

There are no interim analyses planned for this study.

[figure not shown]
#### 2.7 Determination of Sample Size

Due to the public health emergency related to the COVID-19 pandemic during 2020, steps have been taken to ensure patient and practitioner safety in alignment with FDA Guidance dated May 11, 2020 (Guidance on Conduct of Clinical Trials of Medical Products during COVID-19 Public Health Emergency). Most notably, in partnership with clinical sites and the IRB, optional remote assessment procedures for efficacy and safety endpoints has been implemented to ensure safety and respect localized and elective restrictions. Therefore, the sample size has been increased during the conduct of the study to ensure a sufficient number of subjects in the mITT population used in the assessment of the primary effectiveness endpoint.

The study was initially planned to enroll a total sample size of approximately 238 subjects; approximately 204 randomized to treatment with Restylane-L ( $\sim$ 102 injected using needle, and  $\sim$ 102 injected using cannula) and approximately 34 randomized to no treatment.

Based on information on missing data and the number of remote visits performed at study sites so far, the study is now planned to enroll approximately 329 subjects; approximately 282 will be randomized to treatment with Restylane-L (~146 will be injected using needle, and ~136 will be injected using cannula) and approximately 47 will be randomized to no treatment in order to achieve the required number of mITT subjects in each stratum.

2022-08-17 17:26

#### 2.8 Changes in the Analysis from Previous Protocol Versions

Refer to Section 2.4 for a brief background on changes in the analyses specified in the SAP that differ from previous versions of the Protocol Version 10.0 now matches the SAP.

#### 2.9 Change History

The table below outlines the changes made to the SAP since the previous version.

Table 3. Changes from Previous Version

Version	Date	Description of Changes
2.0	06 OCT 2020	
 
Increased the number of subjects to be randomized
 
Added the mITT analysis population
 
Included the new COVID-19 protocol deviation categories
 
Updated the planned protocol deviation analysis
 
Updated the primary analysis method to be conducted using the mITT population
 
CCI
 
Updated the missing data sensitivity analyses to include: CCI
 
BOCF, ITT observed cases, tipping analysis using the mITT population, tipping point analysis using the ITT population
 
Added type of Month 3 visit (onsite, remote) as another subgroup analysis of the primary endpoint
 
Updated the sample size calculation
 

3.0	16 DEC 2021	Updated the MI methods for CMH test (Appendix H)     Updated primary analysis and secondary GIHS analysis method to be the CMH test  CCI

GALDERMA  Title  43USTT1904 Statistical analysis plan - Tear Trough	Doc id MA-42205
---	--------------------

2022-08-17 17:26

 
Updated Snellen Visual Acuity analysis
 
Added Section 2.3.2.1 to describe out of window visit duration analysis
 
Added information to Table 2
 
Added handling of data for injection characteristics, extent of exposure, and diary analyses for subjects injected multiple times in a treatment period.
 

 
Included information on statistical methods updates in section 2.4
 
Updated secondary analysis to present Months 3 and 6 after optional treatment as descriptive only
 
Updated tipping point analysis method to CMH
 

Doc id 43USTT1904 Statistical analysis plan - Tear Trough GALDERMA MA-42205

Print date:

2022-08-17 17:26

### 9 Appendix F. Effectiveness Estimands

Endpoints	Attributes									
	Population	Endpoints	Treatments	Intercurrent Events	Statistical Summary					
Primary	mITT Population; includes all randomized subjects that did not have a remote month 3 GIHS assessment ITT Population; includes all randomized subjects PP Population	Responder rate based on the Blinded Evaluators' live assessment of the Galderma Infraorbital Hollows Scale (GIHS), at 3 months after baseline.	Restylane-L vs. Control	Subjects that don't have a Month 3 GIHS response, due to missed visit, missed procedure, or discontinuation prior to visit, Subject has a prohibited treatment/procedure performed prior to Month 3; Subject has an unstable medical history affecting the IOH area	Number and difference in proportion (n, %) of subjects					
Secondary 1	ITT Population	Responder rate based on the Blinded Evaluators' live assessment of the GIHS, at 6, 9, and 12 months after baseline and at 3 and 6 months after optional treatment.	Restylane-L vs. Control	Subjects that don't have a GIHS response at a respective visit, due to missed visit, missed procedure, or discontinuation prior to visit	Number and difference in proportion (n, %) of subjects					
Secondary 2	ITT Population	Proportion of subjects having at least "Improved" on the Global Aesthetic Improvement Scale (GAIS), as assessed live by the Subject and Treating Investigator separately at all follow-up visits after baseline.	Restylane-L vs. Control	Subjects that don't have a GAIS response at a respective visit, due to missed visit, missed procedure, or discontinuation prior to visit	Number and proportion (n, %) of subjects					
ICCI										

17:26

									Print date:	2022-08-17
	G	A L D E R M A	43USTT1	904 Statistic	al analysis pla	n - Tear Troug	h	Doc id MA-42205		
Endpoints		Attributes								
		Population		Endpoints		Treatments	Intercurrent Events		Statistical Summary	
CCI										

Print date: 2022-08-17 17:26

43USTT1904 Statistical analysis plan - Tear Trough

MA-42205

Doc id

### 10 Appendix G. Schedule of Events

Procedure	Visit 1a	Visit1b	Visit 24	Visit34	Visit4	Visit 4a 	Visit4b	Visit4c4	Visit5 -7	EOS/ET	Visit Sa 	Visit8b t	Visit8c4	Visit 8df	Visit 8e4 EOS for optional Tx
	Visits of combined meets of crite	if subject ligibility	72 hrs after Tx (±24 hrs)	14 days after Baseline (±3 days)	I month  after Baseline (+7 days)	72 hrs after Option al touch- up (±24 hrs)	14 days after Optional touch-up (±3 days)	1 month  after Optional touch-up (+7 days)	after	12 months It (±7 days) after Baseline	72 hrs after optional Tx (±24 hrs)	14 days after optional Tx (±3 days)	l month after optional Tx (+7 days)	3 months 10 after optional Tx (±7 days)	6 months 10 after optional Tx (+7 days)
	Screening Day -30 to 1		TC	Follow-up	Follow-up Optional TU	TC	Follow-up	Follow- up	Follow-up	Follow-up Optional Tx	TC	Follow-up	Follow-up	Follow-up	Follow-up
Informed Consent	x														
Med. Hx/prior therapies	X	X 													
Demographics	X	- 1													
Height/Weight 		X 1.6		X 	X 		X 	X 	X 	X 		X 	X 	X 	X 
Inclusion/Exclusion Criteria	X	X1,2			X 					X1.5					
Urine pregnancy test 	X	X1,2			XIJ					X1,3					
Vision Function Assessments	X	X2.8.9		X	X13.0		X			Xii		X			
Randomization		X													
Treatment with study product		X°			X5,9					X 					
Evaluate device deficiencies		X			X9					X3					
Dispense Subject Diary		X9			X 					X 					
Collect / Review Subject Diary			X 	X	X°	X7	X	Х			X 	X	X		
2D Photography		Xt		X	Xt		X	X	X	X1		X	X	X	X
Concomitant Therapies	X	$X^2$	X	X	X	X	X	X	X	X	X	X	X	X	X
Assessment of AEs		X	X	X	X	X	X	X	X	X	X	X	X	X	X
Treating Investigator Assessments															
GAIS					XI			X	X	XI			X	X	X
GIHS	X	$X^{1,1}$			Xt					X 					
Blinded Evaluator Assessments															
GIHS	X	X 							X	X1				X	X
Subject Assessments	•														
GAIS					Xì			х	х	Xl			х	х	X
CCI															

Prior to any planned treatment

Omitted if the screening and baseline visits occur on Day 1. Screening visit and baseline visit can be combined if no drug washout is needed.

For females of childbearing potential

\*Visit is scheduled only if mitial treatment, optional touch-up or optional treatment is performed

Omitted if optional touch-up or optional treatment is not performed

Subject self-reported. Height only needs to be collected at baseline

Review diary with subject over the phone

Performed prior and 30 minutes post injection of study product

For subjects randomized to study treatment

One month is defined as 4 weeks in the study

ET = Early Termination

EOS = End of Study

GIHS = Galderma Infraorbital Hollows Scale

GAIS = Global Aesthetic Improvement Scale

TC= Telephone call

TU = Touch up

Tx = Treatment

Effective date: 2021-12-1713:25

Title 43USTT1904 Statistical analysis plan - Tear Trough

Doc id

Print date:

MA-42205

2022-08-17 17:26

CCI		

Doc id 43USTT1904 Statistical analysis plan - Tear Trough GALDERMA MA-42205

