	
All incidences of visual disturbances, regardless of relationship to study product or seriousness, are considered Adverse Events of Special Interest (AESIs) and include but are not limited to the following: any change in vision, any loss of vision, blurry vision, double vision, pain in or around the eye, blind spot or shadow in the visual field, trouble moving eyes, any change in Snellen visual acuity including change of one line or greater.
 
Vision Function Assessment tests will be performed prior to and 30 minutes post injection of the study product.
 
A subject diary will be dispensed to all subjects for daily completion over the first 28 days after each treatment to record the following pre-identified symptoms: bruising, redness, pain, tenderness, lumps/bumps, itching, swelling. Any other symptoms outside the pre-identified should also be recorded in the diary. The diary will also include instructions for the subject to:
 
 • Contact an eye doctor (retinal specialist or ophthalmologist) if they experience changes in vision (i.e. vision loss, blurriness, double vision, pain in or around eye, blindness, blind spots, problems moving your eyes), change in skin color, or crusty/scabby skin around the eyelids • Call 911 and seek immediate medical attention if signs of stroke or subject experience dizziness, confusion, weakness, or numbness in face, arms or legs, changes to consciousness or alertness, difficulty speaking/speech impairment, face droop 
Stopping rules Enrollment and treatment in the study will be temporarily halted if an SAE occurs for a vascular embolic event that leads to skin necrosis, vision loss, or stroke, and is determined by the Investigator to be directly or possibly related to the investigational device or injection procedure. The SAE will be investigated by the Sponsor.

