- Planned surgery including dental implants, tooth extractions, orthodontia are prohibited.
- Participation in any other clinical study during this study is prohibited.

If a prohibited therapy becomes a necessary treatment for the safety or best interest of the subject, the Sponsor Medical Expert should be notified, time permitting, to discuss possible alternatives prior to administration of a prohibited therapy.

If a subject receives prohibited therapy during the clinical study, the Sponsor should be notified to discuss the pertinence and the modalities for the subject to continue in the clinical study.

Effective

Version: 10.0

	Title 43USTT1904 CSP Infraorbital Hollows	Doc id MA-40833
---	---	---------------------------

Table 1: Schedule of events

Procedure	Visit 1a	Visit 1b	Visit 2 ⁴	Visit 3 ⁴	Visit 4	Visit 4a ⁴	Visit 4b ⁴	Visit 4c ⁴	Visit 5 -7	Visit 8 or EOS/ET	Visit 8a ⁴	Visit 8b ⁴	Visit 8c ⁴	Visit 8d ⁴	Visit 8e ⁴ EOS for optional Tx	
	Visits may be combined if subject meets eligibility criteria		72 hrs after Tx (±24 hrs)	14 days after Baseline (±3 days)	1 month ¹⁰ after Baseline (+7 days)	72 hrs after Optional touch-up (±24 hrs)	14 days after Optional touch-up (±3 days)	1 month ¹⁰ after Optional touch-up (+7 days)	3, 6, & 9 months ¹⁰ after Baseline (±7 days)	12 months ¹⁰ (±7 days) after Baseline	72 hrs after optional Tx (±24 hrs)	14 days after optional Tx (±3 days)	1 month after optional Tx (+7 days)	3 months ¹⁰ after optional Tx (±7 days)	6 months ¹⁰ after optional Tx (+7 days)	
	Screening Day -30 to 1	Baseline/ Tx Day 1	TC	Follow-up	Follow-up Optional TU	TC	Follow-up	Follow-up	Follow-up	Follow-up Optional Tx	TC	Follow-up	Follow-up	Follow-up	Follow-up	Follow-up
Informed Consent	X															
Med. Hx/prior therapies	X	X ^{1,2}														
Demographics	X															
Height/Weight ⁶		X ^{1,6}		X ⁶	X ⁶		X ⁶	X ⁶	X ⁶	X ⁶		X ⁶	X ⁶	X ⁶	X ⁶	
Inclusion/Exclusion Criteria	X	X ^{1,2}			X ^{1,5}					X ^{1,5}						
Urine pregnancy test ³	X	X ^{1,2}			X ^{1,5}					X ^{1,5}						
Vision Function Assessments	X	X ^{2,8,9}		X	X ^{5,8,9}		X			X ^{5,8}		X				
Randomization		X														
Treatment with study product		X ⁹			X ^{5,9}					X ⁵						
Evaluate device deficiencies		X			X ⁹					X ⁵						
Dispense Subject Diary		X ⁹			X ⁵					X ⁵						
Collect / Review Subject Diary			X ⁷	X	X ⁹	X ⁷	X	X			X ⁷	X	X			
2D Photography		X ¹		X	X ¹		X	X	X	X ¹		X	X	X	X	X
Concomitant Therapies	X	X ²	X	X	X	X	X	X	X	X	X	X	X	X	X	X

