4.7.2 Visit 1b: Baseline/Day 1 (Initial Treatment)

The screening visit and baseline visit (Day 1) may be performed on the same day if a subject is deemed eligible by the Treating Investigator.

If Screening visit and Baseline/Day 1 visit are not performed on the same day, the following procedures should be repeated at the Baseline/Day 1 visit:

- Review for changes in medical history and concomitant therapies.
- Re-confirm eligibility criteria.

² Fitzpatrick T.B. (1988). The validity and practicality of sun-reactive skin types I through VI. Arch. Dermatol. 124, 869–871.

	Title 43USTT1904 CSP Infraorbital Hollows	Doc id MA-40833
--	---	---------------------------

- Perform UPT for all females of childbearing potential (prior to treatment). Test result must be negative for the subject to be eligible for study treatment.
- Assess GIHS – Treating Investigator and Blinded Evaluator
- Evaluate the subject for AEs since screening visit.

Once the subject is deemed eligible for study treatment by the Treating Investigator, the following procedures should be completed:

- Record subject's height and weight.
- Obtain pre-treatment photographs of the infraorbital hollows.
- Randomize the subject to treatment (using needle or cannula according to what is agreed per site) or to no treatment. For subject randomized to treatment:
 - Perform Vision Function Assessments prior to injection.
 - Subjects will be injected with the study product.
 - Record all concomitant medications/procedures used during the injection session.
 - Record the number of syringes used and the volume of study product injected during the injection session.
 - Evaluate for device deficiencies. If deficiencies are noted, complete form as specified in section 8.6
 - Following 30 minutes after injection, perform Vision Function Assessments
 - Evaluate post-treatment AEs by Treating Investigator
 - Dispense Subject Diary and instruct subject on Diary completion. Remind the subject to bring the diary to next on-site study visit.
 - Schedule the 72 hours (± 24 hours) follow-up phone call (Visit 2) and Visit 3, 14 days (± 3 days) after the Baseline visit (Visit 1b) for subjects randomized to treatment.
- Schedule Visit 4, 1 month (+7 days) after the Baseline visit (Visit 1b).

4.7.3 Visit 2: Follow up 72 hour (± 24 hours) telephone call after Baseline/Day 1

Visit conducted for subjects randomized to treatment only.

- Interview subject regarding any concomitant therapies.

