- Interview subject regarding any AEs that have occurred since receiving treatment. If AEs are reported, notify the Investigator immediately and determine whether subject should return to the site for an unscheduled visit. The Investigator should assess all reported AEs in a timely manner.
- Interview subject regarding the Diary completion and reported events since receiving treatment. Remind subject to complete the Diary daily and bring it to the next on-site visit.
- Remind subject of the next scheduled on-site visit.

	Title 43USTT1904 CSP Infraorbital Hollows	Doc id MA-40833
--	---	---------------------------

Effective date: 2021-12-15 20:29

4.7.4 Visit 3: Follow up visit 14 days (\pm 3 days) after Baseline/Day 1

- Interview subject regarding any concomitant therapies and record subject's weight.
- Interview subject and evaluate any AEs, and post-treatment AEs by Treating Investigator (if randomized to treatment) that have occurred since the last visit.
- Obtain photographs.
- Perform Vision Function Assessments.
- Interview subject regarding the Diary completion and reported events since receiving treatment. Remind subject to complete the Diary daily and bring it to the next on-site visit.
- Remind subject of the next scheduled on-site visit.

4.7.5 Visit 4: Follow-up visit 1 month (+ 7 days) after Baseline/Day 1/ Optional touch-up

- Interview the subject regarding concomitant therapies and record subject's weight.
- Interview subject and evaluate any AEs, and post-treatment AEs by Treating Investigator (if randomized to treatment) that have occurred since the last visit.
- Obtain photographs (if treatment is given, ensure photos are taken prior to injection)
- Assessments to be performed, prior to optional touch-up:
 - GIHS – Treating Investigator
 - GAIS – Treating Investigator and Subject

CCI

- Schedule Visit 5, 3 months (\pm 7 days) after the Baseline visit (Visit 1b).

For subjects randomized to treatment

- Collect and review Subject Diary for subjects randomized to treatment:
 - Review diary entries for completeness and legibility.
 - If the subject handwrites entries on the diary pages, review these entries with the subject and clarify as needed. Record all clarifications on the subject's source documents and record the Diary data into the eCRF.

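### For a combined screening and baseline visit, the schedule's Day 1 vision entry says both to omit the test and to test before and 30 minutes after injection

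*SAP*

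**What the plan says.** Protocol Table 1 has a row "Vision Function Assessments". Its Visit 1a cell is a plain X. Its Visit 1b cell is an X with footnotes 2, 8 and 9, and SAP Appendix G shows the same three markers on that cell.

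- Footnote 2: "Omitted if the screening and baseline visits occur on Day 1". It goes on: "Screening visit and baseline visit can be combined if no drug washout is needed".
- Footnote 8: "Performed prior and 30 minutes post injection of study product".
- Footnote 9 limits the entry to subjects randomized to study treatment.

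Protocol 4.7.2 permits screening and Day 1 on the same date and then gives two separate lists. The first is conditional: "If Screening visit and Baseline/Day 1 visit are not performed on the same day, the following procedures should be repeated" at Day 1. The second applies to every subject randomized to treatment. It has a vision test before injection and, afterwards, "Following 30 minutes after injection, perform Vision Function Assessments".

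The synopsis states the rule without exception: "Vision Function Assessment tests will be performed prior to and 30 minutes post injection of the study product". Protocol 6.5.3 requires the post-injection test, and Protocol 8.2 (which names baseline) and SAP 1.5.2 require both tests, all without a same-day exemption.

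**The concern.** On a combined visit, footnote 2 removes the Visit 1b vision cell while footnote 8 requires two tests in that same cell. A site working from the schedule has conflicting instructions about a safety procedure.

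The test that matters is the one 30 minutes after the Day 1 injection. Protocol 2.4 names vision testing before and after injection as a risk mitigation, and describes visual disturbances after facial filler injection, including blindness, with onset from immediate to a few weeks. Under 8.2.1 a change of one Snellen line or more must be reported to the sponsor within 24 hours as an event of special interest. A change the subject does not notice is found only by testing.

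**Working it through.** There is no planned figure to reproduce. The check compares the schedule with the text and then sizes the consequence.

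**1. Which Visit 1b cells carry footnote 2, and does 4.7.2 treat them as separate-day repeats?** The cells are from Protocol Table 1.

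| Visit 1b cell with footnote 2 | In the 4.7.2 separate-day list? |
|---|---|
| Medical history / prior therapies | Yes |
| Inclusion/exclusion criteria | Yes |
| Urine pregnancy test | Yes |
| Concomitant therapies | Yes |
| GIHS, Treating Investigator | Yes |
| GIHS, Blinded Evaluator | Yes |
| Vision function | No: it is in the list for all subjects randomized to treatment |

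Six of 7 match, and vision is the one that does not. It is also the only one of the seven that includes a post-injection procedure. The match is not exact in the other direction: the separate-day list also includes adverse events since screening, whose Visit 1b cell has no footnote 2. Adverse events are not marked at Visit 1a, so a same-day repeat does not arise for them.

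**2. What does each footnote give for a treated subject with a combined visit?**

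- Footnote 2 read literally: no Visit 1b vision test.
- Footnotes 8 and 9: two tests, one before injection and one 30 minutes after.
- The Visit 1a test on the same day can serve as the pre-injection test.
- No other cell supplies the 30-minute test, so the conflict remains for that test.

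**3. Which injection sessions are affected?** There are three possible sessions: Day 1, the optional touch-up at month 1 and the optional treatment at month 12. In Protocol Table 1 the vision cell has footnotes 5, 8 and 9 at Visit 4 and footnotes 5 and 8 at Visit 8. Footnote 2 is on neither. The conflict is confined to 1 of 3 sessions.

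**4. When is the next scheduled vision test if the Day 1 post-injection test is skipped?** Visit 2 is a telephone call with no vision test. Visit 3 is 14 days after baseline, plus or minus 3: 14 − 3 = 11 and 14 + 3 = 17, so 11 to 17 days.

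**5. To how many subjects does the entry apply?** Planned treated subjects: 146 (needle) + 136 (cannula) = 282. With s the share of combined visits, the number is 282 × s. The documents do not give s. Over s = 0 to 1 the range is 0 to 282. This counts subjects to whom the conflicting entry applies and does not estimate missed tests.

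**The case against.** The strongest reply is that the documents already settle the matter. Section 4.7.2 is the operative visit instruction and requires both tests for every treated subject with no same-day exemption; the synopsis, 6.5.3, 8.2 and SAP 1.5.2 agree on the post-injection test. Footnote 2 sits only on items also marked at Visit 1a, so it can be read as a do-not-repeat note: the screening test serves as the pre-injection test, and the 30-minute test, which repeats nothing, stays. On that view this is a drafting slip with no demonstrated consequence. Other cover also exists: Day 1 adverse event evaluation, the 72-hour call, diary advice to contact an eye doctor, and 24-hour reporting of events of special interest.

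Most of this stands, and it is why the point is minor. The do-not-repeat reading is probably what was meant. But the footnote's words omit the whole cell and do not separate the pre-injection part from the post-injection part. Nor can sites rely on the visit text alone for vision testing: 4.7.1 does not list the screening vision test that Table 1 marks at Visit 1a and that inclusion criterion 3 needs. The schedule has to be right here.

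It is also fair that the SAP copy directs no site conduct, and that 0 to 282 says little beyond the size of the treated arm.

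**Conclusion.** The concern holds: the Visit 1b vision entry is wrong as written for a combined visit, at low severity. The error is one cell, appearing in two documents and affecting 1 of 3 injection sessions. The firm part of the conflict is the 30-minute test after the Day 1 injection; the pre-injection test is covered by the same-day screening test. If that post-injection test were skipped, scheduled vision testing would resume 11 to 17 days after baseline.

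No missed test is shown. Eligibility, the pre-injection baseline, the sample size and the effectiveness analyses are unaffected. The conclusion rests on the footnote markers as read, which agree between the protocol and the SAP for this cell. It needs no assumption about how often visits were combined.

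**What to change.** In Protocol Table 1 and SAP Appendix G, change the footnotes on the Visit 1b vision cell from 2, 8, 9 to 8, 9. This matches what 4.7.2 already asks of every treated subject, so it adds no new requirement.

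If the sponsor wants to avoid a second pre-injection test on a combined day, replace footnote 2 on this cell only with: *If screening and baseline are combined, the screening test serves as the pre-injection test; the 30-minute post-injection test is always done in treated subjects.* If this option is chosen, 4.7.2 should say the same.

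Either version secures the post-injection test. The cost is wording only, with no change to data, sample size or analysis.
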